### 9.2 Statistical analysis

All quantitative variables will be tested for normal distribution according to the Kolmogorov-Smirnov test. Statistical analyses will be performed via the SPSS statistical software package,

applying a significance level of  $\leq 0.05$ . Continuous variables will be expressed as mean  $\pm$  SD. Comparisons will be done with paired t-, Wilcoxon rank signed, Mann-Whitney U- or Kruskal-Wallis test when appropriate. The chi-square test will be applied for categorical variables and results will be expressed as n (%). Analysis will be performed to compare the intra-coronary measurements (FFR, RFR, IMR) prior to intervention (group 1) versus 6 months after intervention (group 2). Descriptive statistics (mean/median, standard deviation and percentiles for continuous data; percentage for categorical data) and graphical representation (boxplots, histograms and density plots) will be used to compare both groups' characteristics. Intra-coronary measurements in both groups will then be compared and tested using statistical tests (paired t-, Wilcoxon rank signed test). The correlation between FFR and RFR will be analyzed using Pearson correlation coefficient. The diagnostic performance of RFR in indicating SPECT myocardial ischemia will be evaluated using receiver operating characteristic (ROC) curve analysis.

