## PROTOCOL SUMMARY

Aortic stenosis (AS) is the most common primary valve disease leading to surgery or catheter intervention in Europe, with a growing prevalence due to the aging population. Severe AS is associated with significant morbidity and mortality and is treated by surgical valve replacement (SAVR) or transcatheter aortic valve implantation (TAVI). However, significant coronary artery disease (CAD) is reported in more than 60% of patients with AS, and this concomitant CAD needs to be correctly assessed because untreated significant CAD is associated with adverse outcomes. Current guidelines recommend intra-coronary pressure measurement using either fractional flow reserve (FFR) or non-hyperemic pressure ratios (NHPR) for the assessment of intermediate coronary artery lesions before revascularization. However, correctly identifying hemodynamically significant coronary stenoses by FFR or NHPR is difficult in patients with AS because of the hypertrophic remodeling related to the valve pathology, which interferes with coronary blood flow in the microcirculation and reduces the accuracy of FFR and NHPR. This has resulted in substantial controversy in this field of coronary artery disease and there is currently no clear guideline for the management of AS patients with concomitant CAD. Recent technological advances now permit the concomitant evaluation of FFR/NHPR and microcirculatory function at the time of cardiac catheterization. Using this technology, we will simultaneously evaluate the hemodynamic significance of coronary stenoses (using FFR and a NHPR - Resting Full cycle Ratio [RFR]) and the microcirculatory function (Index of Microcirculatory Resistance, IMR) in patients with AS and CAD prior to SAVR/TAVI. One hundred patients with AS and intermediate CAD will be included in the study. Of them Eighty will undergo AVR and at least 58 will undergo the follow-up at 6 Months. During routine pre-valve replacement cardiac catheterization, measurement of intermediate CAD lesions (by FFR and RFR) and IMR will be performed in duplicate using new software. These measures of CAD severity will be compared with a gold standard non-invasive test (single photon emission computed tomography [SPECT]). This will validate the use of RFR and determine if IMR can be used to improve the ischemia prediction of FFR. In addition, the patients undergoing TAVI the LVEDP will be measured immediately before and after valve implantation and FFR, RFR and IMR will be measured after valve implantation. Subsequently, when these patients undergo a post-intervention (whether SAVR or TAVI) evaluation 6 months after valve replacement, the effect of valve replacement on FFR, RFR and IMR (again in duplicate) will be determined. This will be the first study measuring these parameters before and 6 months after valve replacement. The data will be used to calculate a 'corrected' FFR (or RFR) based on microcirculatory function in these patients, which can then be used in the future to correctly evaluate CAD pre-intervention in patients with AS. This will translate into more efficient management of patients with AS. Fewer of these patients will unnecessarily undergo coronary artery bypass grafting or stenting when the CAD does not need to be treated and, conversely, in those who do require treatment of the CAD, revascularization can be carried out during a single surgery/intervention, avoiding multiple high risk procedures in patients who are already at high peri-operative/peri-interventional risk.

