AS and intermediate CAD. They determined that the optimal iFR threshold for detecting ischemia compared with  $^{99m}\text{Tc}$  single-photon emission computed tomographic (SPECT) myocardial perfusion imaging was 0.82, while the cut-off for FFR was 0.83. This is in contrast to the large, outcome-based randomized controlled studies in patients without AS, and different to the current guideline cut-offs of  $\leq 0.89$  for resting indices and  $\leq 0.80$  for FFR. The RFR threshold for detecting ischemia has not yet been determined in patients with AS.

A more comprehensive study with performance of intra-coronary measurements before and after TAVI may help determine the effect of adverse LV remodelling and microvascular dysfunction on the hemodynamic measurement of coronary artery lesions in patients with severe AS. However, the timing of the follow-up measurements has not been clearly defined. Several studies have performed acute measurements pre- and post-TAVI but no invasive study (measuring FFR and/or resting indices) has been performed after allowing adequate time for reverse remodelling in order to really determine the effect of microvascular reverse remodelling on intra-coronary hemodynamic measurements. Exactly how long is needed after TAVI to ensure adequate myocardial and microvascular remodelling has occurred in order to appropriately use intra-coronary hemodynamic measurements is not known at this stage. One MRI-based study demonstrated a significant reduction in indexed LV mass from  $76\text{g}/\text{m}^2$  to  $68\text{g}/\text{m}^2$  within a few days. In another study, echocardiographic ejection fraction and LV global longitudinal strain improved significantly when measured 10 days after TAVI. However, indexed LV mass improvement was only significant during long-term (months-to-years) follow up. In a more recent, echocardiographic-based study, indexed LV mass decreased from  $117\text{ g}/\text{m}^2$  to  $100\text{ g}/\text{m}^2$  in a surgical aortic valve replacement (SAVR) group and  $114\text{ g}/\text{m}^2$  to  $108\text{ g}/\text{m}^2$  in a TAVI group after 3 months with further reductions at one year. Whether these global changes in LV remodelling translate into improvements in microvascular function, and hence improve the diagnostic accuracy of FFR is not yet known.

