### Secondary outcomes

2. Measurement of IMR in patients with AS prior to intervention and 6 months after SAVR/TAVI.
  - a. Description of the range of IMR values in a cohort of patients with severe AS.
    - i. Do all patients with severe AS have high microvascular resistance as assessed by IMR?
    - ii. Does IMR change significantly 6 months after TAVI/SAVR? If there is a significant decrease in IMR then this indicates that microcirculatory function improves 6 months after aortic valve intervention.
3. Null hypothesis: the “corrected” FFR (at baseline; based on baseline IMR) does not correlate with the post-intervention FFR.
  - a. If the null hypothesis is upheld then a correction of FFR using baseline IMR does not improve the validity of FFR in patients with severe AS.
4. Null hypothesis: using IMR at baseline does not improve the ischemia prediction of FFR. Ischemia is measured by SPECT (Figure 2).
  - a. If the null hypothesis is upheld then IMR does not improve stratification of coronary ischemia based on FFR.

- b. If a significant proportion of patients with SPECT ischemia have a raised IMR this would support the hypothesis that IMR can be used to correct falsely high (negative) FFR measurements.
- 5. Comparison of the diagnostic performance of FFR and RFR with SPECT ischemia (and compare with findings of Yamanaka *et al*).
- 6. Reproducibility of the FFR, RFR and IMR

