## Secondary outcomes

- 1. A description of the range of IMR values in a cohort of patients with severe AS will be a novel and important contribution to the field of interventional cardiology. Furthermore, the change in IMR (microvascular function) in response to valve replacement will be an important finding in this study. If there is a significant decrease in IMR then this indicates that microcirculatory function improves 6 months after aortic valve intervention. Since microvascular function predicts outcomes in patients with AS, IMR evaluation at 6 months after TAVI/SAVR might provide an additional method to risk stratify these patients even after correction of the valve pathology.
- 2. If the “corrected” FFR (at baseline; based on baseline IMR) does not correlate with the post-intervention FFR then a correction of FFR using baseline IMR does not improve the accuracy of FFR in patients with severe AS.
- 3. Compared with SPECT, a correlation of FFR and RFR will be an important contribution. Firstly, this will be a validation of RFR as a resting measure of ischemia in AS patients. Secondly, these data will support the data of a previous study with a different resting measure of ischemia (iFR) or the findings may be in conflict with the previous study, which would be important.

4. Using SPECT as a standard of myocardial ischemia, IMR may improve the ischemia prediction of FFR. This would be an extremely important finding, supporting the routine use of IMR in patients with microvascular disease when coronary artery lesions need assessment by FFR. Because AS is an important clinical condition with reversible microvascular dysfunction, this provides an excellent naturally occurring model for the study of microvascular function and CAD. These findings will be useful in other groups of patients who also have microvascular dysfunction (including patients with heart failure, obesity, diabetes, liver disease, chronic kidney disease and heart transplant patients). Being able to factor-in microvascular dysfunction (using simultaneously measured microvascular resistance) at the time of FFR measurement will permit accurate assessment of the severity of CAD in these patients. This study has the potential to revolutionize the assessment of coronary artery lesions, not just in patients with AS, but in all patients with CAD since the validity of CAD assessment by FFR/NHPRs may, indeed, depend on microvascular function.

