## 9. STATISTICS AND ANALYSIS

### 9.1 Sample Size

The sample size for the ***primary objective*** (change in FFR after aortic valve intervention) is based on previous measurements of FFR in patients with aortic stenosis, where a standard deviation of the data was reported. An expected mean FFR of 0.82 with a standard deviation of 0.08 was used in the calculation. Fifty eight (58) patients with pre- and post-interventions catheterizations will be sufficient to detect a reduction in the FFR from 0.82 to 0.79 with an alpha level of 0.05 and power of 0.80. A total sample of 100 patients with baseline measurements of which 80 patients will undergo (T)AVR without revascularisation (20% will undergo revascularisation) and in this way are eligible for pre-and post-intervention catheterization will allow for a 25 % drop-out during the follow-up phase of the study. Missing values will predominantly be at random. Therefore, the primary endpoint will be assessed using complete case analysis. To account for missing values, the number of patients will be increased from 58 to 80 (since missing data will be excluded from analysis).

For the ***secondary objective*** (comparison of FFR versus RFR): approximately 10-20% will have left main CAD, triple vessel disease, prior myocardial infarction or tandem lesions and will not be eligible for SPECT. One Hundred patients with baseline measurements will allow a 20% drop-out to end up with 80 patients with both baseline SPECT and invasive measurements. Yamanaka *et al.* found that a sample of 80 patients was necessary to determine the optimal cutoff value of iFR for indicating myocardial ischemia. Since RFR and iFR have an extremely high correlation (0.99), the same number of patients (80) is expected to achieve an area under the ROC curve of 0.70 with 0.90% power at a significance level of 0.05 in a 2-sided test.

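### Section 9.2 plans a ROC analysis against SPECT for RFR only, although objective 5 covers FFR and RFR; the power that Section 9.1 labels as FFR versus RFR belongs to a single index

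*Combined protocol and SAP*

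**What the plan says.** Secondary outcome 5 in the Study Objectives, repeated as secondary endpoint 5 in the synopsis, reads "Comparison of the diagnostic performance of FFR and RFR with SPECT ischemia". The Study Objectives version adds that the findings will be compared with those of an earlier SPECT study in aortic stenosis. The Protocol Summary has the same intent. After naming FFR, RFR and IMR it states: "These measures of CAD severity will be compared with a gold standard non-invasive test". Item 3 of the expected secondary outcomes says: "Compared with SPECT, a correlation of FFR and RFR will be an important contribution".

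Section 9.2 contains one diagnostic-performance analysis: "The diagnostic performance of RFR in indicating SPECT myocardial ischemia will be evaluated using receiver operating characteristic (ROC) curve analysis". FFR appears in that section in two other roles only: the tests before versus 6 months after valve replacement, and "The correlation between FFR and RFR will be analyzed using Pearson correlation coefficient".

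Section 9.1 labels the secondary sample size "comparison of FFR versus RFR", and the Timeline in Section 4 uses a similar label. The justification takes 80 patients from an earlier study of the iFR cut-off, carries the number to RFR through an RFR-iFR correlation of 0.99, and concludes that "the same number of patients (80) is expected to achieve an area under the ROC curve of 0.70 with 0.90% power" at a two-sided level of 0.05. The printed percentage is evidently meant as 90%.

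The Background reports from the earlier study an iFR cut-off of 0.82, "while the cut-off for FFR was 0.83".

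**The concern.** The objective names two indices and the analysis section evaluates one. A correlation between FFR and RFR shows how closely the two agree. It does not involve SPECT, so it cannot show how well either detects ischemia or which does so better.

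Two things are at stake. First, half of objective 5 has no planned analysis, and the promised comparison with the earlier study cannot be made for FFR. An FFR ROC curve added later would be unplanned, with its method and cut-off rule open to choice after the data are seen. FFR is also the index of the primary endpoint. Second, a reader of Section 9.1 could take the 90% power as applying to FFR versus RFR, when the calculation contains no second AUC, no AUC difference and no correlation between FFR and RFR.

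**Working it through.** **Step 1: objective against analysis.**

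| Element of objective 5 | Analysis in Section 9.2 |
|---|---|
| RFR against SPECT | ROC analysis |
| FFR against SPECT | none |
| FFR compared with RFR on accuracy | none (Pearson correlation, without SPECT) |
| Comparison with the earlier study's FFR cut-off (0.83) | not possible without an FFR ROC curve |

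Figure 2 is not available for this review. Its legend names no analysis of FFR against SPECT in this study.

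**Step 2: reproduce the stated 80 patients.** Inputs from Section 9.1: AUC A = 0.70, N = 80, two-sided 0.05, power 90%. Assumed, because the plan does not give them: null AUC 0.50 and the share of SPECT-positive patients. With n1 positive and n0 negative patients:

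- Hanley-McNeil variance: [A(1−A) + (n1−1)(Q1−A²) + (n0−1)(Q2−A²)] / (n1·n0), where Q1 = A/(2−A) and Q2 = 2A²/(1+A).
- Null SE: √[(n1+n0+1)/(12·n1·n0)].

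At 40/40, Q1 = 0.5385 and Q2 = 0.5765. The variance is [0.21 + 39(0.0485) + 39(0.0865)]/1600 = 0.00342, so the SE is 0.0585. The null SE is √(81/19200) = 0.0650. With the null SE for the critical value, power = Φ[(0.20 − 1.96×0.0650)/0.0585] = 0.893. With the alternative SE throughout, power = Φ[0.20/0.0585 − 1.96] = 0.928.

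| SPECT-positive / negative | Power, null SE for critical value | Power, alternative SE throughout |
|---|---|---|
| 16/64 (20%) | 0.698 | 0.717 |
| 24/56 (30%) | 0.818 | 0.845 |
| 32/48 (40%) | 0.873 | 0.903 |
| 40/40 (50%) | 0.893 | 0.928 |
| 48/32 (60%) | 0.886 | 0.932 |

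With the first method, 90% power needs 82 patients at 50% positive, 102 at 30% and 135 at 20%. So 80 fits a one-index test near balance. The figure describes one AUC against chance.

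**Step 3: precision of a paired FFR-RFR difference.** Half-width of the 95% CI = 1.96 × √[2(1−r)] × SE, where r is the correlation between the two AUC estimates (assumed) and both AUCs are 0.70. At 40/40 and r = 0.8: 1.96 × √0.4 × 0.0585 = 0.072.

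| Positive/negative | r = 0.5 | r = 0.7 | r = 0.8 | r = 0.9 |
|---|---|---|---|---|
| 32/48 | 0.120 | 0.093 | 0.076 | 0.054 |
| 40/40 | 0.115 | 0.089 | 0.072 | 0.051 |
| 48/32 | 0.114 | 0.088 | 0.072 | 0.051 |

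Here r is not the correlation between the indices themselves. In a binormal simulation (4,000 runs, DeLong), a within-group correlation of 0.8 between FFR and RFR gave an AUC correlation of 0.76-0.78 and a half-width of about 0.08. A within-group correlation of 0.9 gave about 0.88 and about 0.06.

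**Step 4: power for a paired difference.** Simulated DeLong test, 80 patients, 40-60% positive, illustrative difference of 0.10:

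| Within-group correlation | AUC 0.70 vs 0.60 | AUC 0.80 vs 0.70 |
|---|---|---|
| 0.6 | 40-43% | 46-48% |
| 0.7 | 49-51% | 57-59% |
| 0.8 | 64-67% | 73-75% |
| 0.9 | 90% | 94-95% |

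**The case against.** The strongest reply is that objective 5 may mean each index against SPECT, not a test of one against the other; the Protocol Summary supports that reading. This stands, and it makes the paired comparison the lesser part of the point. The head-to-head reading rests mainly on the labels in Section 9.1 and the Timeline. Under either reading the FFR ROC curve is missing.

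Second, Section 9.1 is open about its source: anyone who reads to the end sees a calculation from an iFR study for one AUC. That also stands. This half is a labelling fault, and 80 is not shown to be wrong.

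Third, the paired power depends on assumptions outside the plan. By the Hanley-McNeil approximation at 40/40, a difference of 0.15 (AUC 0.70 vs 0.85) would have 81%, 88% and 95% power at AUC correlations of 0.5, 0.6 and 0.7. A difference of 0.05 would have only 50% even at 0.9. The figures therefore show that the 90% is not transferable; they do not show that the comparison must fail.

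Fourth, Figure 2 is cited in objective 4, on FFR, IMR and SPECT, and might depict FFR against SPECT. Section 9.2 also allows a Mann-Whitney test where appropriate. Neither specifies an AUC or a cut-off for FFR.

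Finally, this is a secondary objective and no data are lost. That limits the weight of the point, but it is also why the correction is cheap.

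**Conclusion.** The concern holds. As written, Section 9.2 leaves the FFR half of objective 5 without an analysis, and the power in Section 9.1 does not belong to the comparison named in its label. The single-index figure is sound near balance: 87-93% power with 80 patients at 40-60% SPECT-positive, falling to 82-85% at 30% and 70-72% at 20%, all against an assumed null AUC of 0.50. A paired FFR-RFR difference would be estimated to within about ±0.05 to ±0.12 at 40-60% positive, for AUC correlations of 0.9 down to 0.5. For a difference of 0.10, the 90% carries over only if the indices correlate at about 0.9 within the ischemic and non-ischemic groups. The 0.10 and all the correlations are assumptions. The primary endpoint is unaffected. The change should be made, but the design does not depend on it.

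**What to change.** In Section 9.2, replace the RFR-only sentence with wording such as: *FFR and RFR will each be assessed against SPECT ischemia by ROC analysis in the same patients; the paired difference in AUC (DeLong) will be reported with a 95% CI.* Keep the Pearson correlation as description. If objective 5 is meant only as each index against SPECT, the FFR curve is the essential addition, and the paired difference serves the FFR-versus-RFR label.

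In Section 9.1, add: *This power applies to a single index; the difference between FFR and RFR is estimated, not powered.* Also correct the printed power to 90%, and state the null AUC and the assumed share of SPECT-positive patients.

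The cost is one more ROC curve and one paired comparison. FFR and SPECT are scheduled at baseline in Section 4, and Section 3.8 has RFR measured just before FFR, so no patients or procedures are added. The price is that the paired difference is reported without a power claim. If a patient can contribute more than one lesion, the unit of analysis must also be stated, because the ordinary DeLong interval treats observations as independent; that is a separate matter.

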## 10. REGULATORY REQUIREMENTS

### 10.1 Institutional Review Board and Ethics Committee: IRB/IEC

The clinical investigation plan as well as other study documents required by the ethics committee will be submitted for getting approval from the IRB/IEC.

### 10.2 Insurance

In accordance with the Belgian Law relating to experiments on human persons dated May 7, 2004, Sponsor shall assume, even without fault, the responsibility of any damages incurred by a Study subject and linked directly or indirectly to the participation to the study, and shall provide compensation therefore through its insurance.

### 10.3 Confidentiality

Patient confidentiality will be maintained throughout the study. It will be ensured that the information can always be tracked back to the source data, if required. Data relating to the study might be made available to regulatory authorities) preconditioned the data are treated confidentially and that the patient's privacy is guaranteed.

## 10.4 Publication Policy

The study results will be disseminated, valorized and published via abstracts and publications in high-index, peer-reviewed journals. Also, the results will be presented at several international (EuroPCR, TCT, etc.) and national (Belgian Society of Cardiology (BSC), Belgian Working Group of Interventional Cardiology (BWGIC) congresses and symposia.

### 1. Intellectual Property

Any Intellectual Property conceived or reduced to practice under this Agreement solely by Principal Investigator, Institution' (UZ Leuven, Belgium) or local study site' employees shall be owned by the Institution ("Institution Intellectual Property"); provided, however, no Institution Intellectual Property shall include Confidential Information provided by the local study sites. To the extent permitted by the policy of a medical-professional journal, medical institution, educational institution, or medical association relating to any publication or presentation of study data or results hereunder, ownership of the copyright in any publication, abstract, or presentation approved under this section will belong to the Institution (UZ Leuven).

